### 1.2. Populations at Increased Risk of SARS-CoV-2 Infection Among Household Contacts of a Person Infected with SARS-CoV-2

Efforts to control the pandemic have resulted in widespread shelter-in-place orders. Transmission of SARS-CoV-2 occurs primarily through person-to-person contact and respiratory droplet transmission (Lai, 2020). Household contacts of a person infected with SARS-CoV-2 are at a high risk for acquiring infection, with transmission rates ranging from approximately 10% to 15%. One US study reported a household attack rate of 29%, 42% among children (<18 years) of the SARS-CoV-2-infected patient, suggesting that children and adolescents are especially vulnerable to household transmission of SARS-CoV-2 (Lewis, 2020). Pregnant women, in particular, are at increased risk for developing severe COVID-19 and have been shown to have a higher rate of hospitalization, need for mechanical ventilation, and ICU admission than non-pregnant women (Ellington, 2020) (Knight, 2020)(Woodworth, 2020). Neonatal transmission of SARS-CoV-2 has also been reported (Vivanti, 2020). Therefore, pregnant women should be considered for inclusion in COVID-19 prophylaxis efforts. Although it has been reported that the majority of individuals who acquire infection from household contacts develop symptoms of COVID-19 (Burke, 2020) (Jing, 2020), (Bi, 2020) (Li, 2020b), in a cruise ship setting, the majority of persons who are asymptomatic at the time of testing remain asymptomatic throughout the course of the infection (ie, until reverse transcription polymerase chain reaction (RT-PCR) results are negative (Sakurai, 2020). Prophylaxis is urgently needed to reduce transmission rates and/or reduce the occurrence of symptomatic disease. Ideally, prophylaxis would need to be given as soon as possible after a known exposure, as the duration of time between symptomatic infection in the source individual and the development of symptoms in newly infected individual is thought to be approximately 5 days, with a possible range of 2 to 14 days (Lauer, 2020) (Li, 2020a). Animal models suggest that SARS-CoV-2 RT-PCR in nasopharyngeal (NP) samples become positive within a few days after infection (Rockx, 2020). An ideal agent for prophylaxis should be fast acting and highly effective and should protect against multiple viral variants. A monoclonal antibody (mAb) combination therapy, with two different monoclonal antibodies that bind distinct regions of the portion of the

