### 3.2.2. Subject Population

The study population will consist of approximately 3500 adult and adolescent subjects and approximately 250 pediatric subjects <12 years old, with household contact exposure to individual with a confirmed SARS-CoV-2 infection. In this study, the household contact must share the same residence and have a close exposure to the first individual in the household with a known SARS-CoV-2 infection (index case). In the case where more than 1 index case is the first known SARS-CoV-2 infected individual in the household (eg, 2 people are tested at the same time), this is allowed, and 1 index case should be chosen, at the discretion of the investigator, to be labeled “index case” in the household CRF. The study was originally planned to enroll 2000 adult and adolescent subjects. However, a blinded analysis of approximately 25% of enrolled subjects in this study was performed, demonstrating that higher than expected seropositivity was observed in cohort A. Therefore amendment 4 for the protocol increased the sample size for the study to account for the higher than expected seropositivity in cohort A. Amendment 5 for the protocol increased the sample size further to accommodate the administrative assessment of assumption verification and sample size estimation.

A household is defined as a group of people who live together at the same residence and share multiple living spaces (eg, living room, bedroom, kitchen, bathroom). In case there is uncertainty that the characteristics of the residence meets the definition of a ‘household’, the investigator and the Regeneron Medical Monitor should discuss prior to randomization.

To be included in the study, subjects must be randomized within 96 hours of collection of the index cases’ positive SARS-CoV-2 diagnostic test sample. Household contacts of individuals infected with SARS-CoV-2 are at a high risk for acquiring infection, with transmission rates ranging from approximately 10% to 15% in these settings (Burke, 2020) (Jing, 2020) (Li, 2020b). Therefore,

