approximately 15% of subjects were expected to develop symptomatic disease in follow-up after a household contact transmission event (Li, 2020b). A minority of subjects were expected to be seropositive at baseline, as seropositivity in the general population, outside of hard-hit areas like New York City, was expected to be less than 10% (Burke, 2020). Upon blinded review of approximately the first 25% of subjects enrolled into this study, baseline seropositivity rates in cohort A subjects were approximately 3 times higher than anticipated and a minority of cohort A subjects who became infected during the 28 day efficacy assessment period were symptomatic. Subjects with positive rapid SARS-CoV-2 RT-PCR at the time of randomization, who are either seronegative or seropositive at baseline will also be included in the study, but only subjects who are both seronegative and negative for SARS-CoV-2 infection by central lab RT-qPCR at baseline will be included in the primary efficacy analysis.

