### 3.2.5. Primary Objective

The primary objectives of this study are:

- Cohort A: To evaluate the efficacy of REGN10933+REGN10987 compared to placebo in preventing symptomatic SARS-CoV-2 infection (broad-term) confirmed by RT-qPCR in asymptomatic subjects at risk who are seronegative at baseline.
- Cohort B: To evaluate the efficacy of REGN10933+REGN10987 compared to placebo in preventing COVID-19 symptoms (broad-term) in asymptomatic subjects that are SARS-CoV-2 RT-qPCR positive and seronegative at baseline.

The FDA Guidance on COVID-19 recommends that in prevention trials, the primary endpoint should be the occurrence of laboratory-confirmed SARS-CoV-2 infection, with or without symptoms. A descriptive administrative analysis of seronegative subjects in cohort A (n=409) demonstrated a 100% reduction in broad-term symptomatic PCR-positive infection with 8/223 (3.6%) placebo treated subjects developing symptomatic infection versus 0/186 (0%) REGN10933+REGN10987 treated subjects; OR 0.00 (0.00, 0.69) p<0.01. The revised primary objectives and endpoints for cohort A are informed by these results. Thus, these revisions are applied to objectives and endpoints for cohort B as well. The final primary objectives and endpoints for the completed study will be assessed in the final study population enrolled, excluding those that were already unblinded and assessed in the descriptive administrative analysis (Section 11.4.9). Protocol amendment 6 specifies a single primary objective and endpoint for each cohort which consists of the prevention of laboratory confirmed symptomatic SARS-CoV-2 infection (broad term)(Section 2.1.1.1 and Section 4.1.1).

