**Virologic efficacy:** The primary mechanism of action of REGN10933+REGN10987 is blockade of the S protein RBD interaction with ACE2, leading to inhibition of SARS-CoV-2 host cell infection. The ability of REGN10933+REGN10987 treatment to prevent SARS-CoV-2 infection will be evaluated by SARS-CoV-2 RT-qPCR test results from weekly NP swab samples. Weekly sample collection is considered an adequate collection frequency to ensure early detection of viral load (SARS-CoV-2 RT-qPCR positivity) in infected individuals; this is based on the average duration of viral positivity from NP swabs that ranges from 7 to 28 days (He, 2020) (Wölfel, 2020). All subjects will have SARS-CoV-2 RT-qPCR testing by NP sample. Nasopharyngeal swab testing has been shown to have good sensitivity and specificity for detecting SARS-CoV-2 RNA (Zou, 2020) (Pere, 2020). The administrative assessment of seronegative subjects (n=409) in cohort A demonstrated that the risk of becoming infected (ie, becoming SARS-CoV-2 RT-PCR positive) was reduced as early as the first week of study (10.3% in subjects in the placebo group versus 5.4% in subjects in the REGN10933+REGN10987 group at day 8). The protection continued through the following weeks. Both the magnitude and duration of infection were reduced by REGN10933+REGN10987 treatment. Infections occurring in subjects in the placebo group had, on average, more than 100-fold higher peak viral load. Infections in subjects in the REGN10933+REGN10987 group lasted no more than 1 week, while approximately 40% of infections in subjects in the placebo group lasted 3 to 4 weeks. No infected subjects in the REGN10933+REGN10987 group had high viral loads ( $>10^4$  copies/mL) compared to 62% of the infected subjects in the placebo group (13/21 placebo versus 0/9 REGN10933+REGN10987) (CDC, 2020b). (CDC, 2020b)

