### 11.2. Justification of Sample Size

An administrative assessment for assumption verification and sample size estimation for cohort A was conducted using unblinded descriptive analyses without performing any formal statistical hypothesis testing. Analyses were conducted in the group of cohort A subjects randomized from study initiation through the date of randomization that was associated with approximately 30 RT-PCR events amongst cohort A seronegative subjects during the EAP (subjects overall regardless of baseline serology status [eg, seronegative, seropositive, or other]). The subjects who were evaluated in this descriptive analysis will not be included for the final efficacy analyses, however, these subjects will be included in the safety analyses (Section 11.4.9). To maintain operational efficiencies and because of the progressive rollout of SARS-CoV-2 vaccination which may change the dynamics of virus transmission/infection in the near future, enrollment into the study was not paused while the administrative assessment was performed and was estimated that the total enrollment may reach approximately 3500 subjects. The justification of sample size in cohort A (Section 11.2.1) with the assumption of reduction of symptomatic infection is based on the results from the administrative assessment.

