#### 11.2.1. Cohort A: Adult and Adolescent Subjects ( $\geq 12$ years) Who Are SARS-CoV-2 RT-qPCR Negative at Baseline

In cohort A, subjects are randomized in a 1:1 allocation ratio to REGN10933+REGN10987 or placebo. The primary hypothesis is the reduction in the proportion of symptomatic RT-qPCR (broad-term) confirmed SARS-CoV-2 infections in seronegative subjects. To calculate the sample size required to achieve at least 90% power for seronegative subjects in cohort A, it is assumed that the statistical hypothesis will be tested in a 2-sided test. Based on the administrative assessment results among 409 seronegative subjects in cohort A, a 50% reduction of infections (symptomatic or asymptomatic) compared to the placebo group and a 100% reduction of symptomatic infections compared to placebo group was observed. Due to the small sample size in the administrative assessment, it is assumed, for the purpose of calculating study power, that an approximately 50% reduction or greater in symptomatic infections compared to placebo group will be expected for the final primary efficacy analysis.

In this household study design, the number of subjects per household, the correlation between subjects and symptomatic infection rates within a household are unknown. To detect a relative risk of 0.5 (ie, 50% reduction of the assumed 10% attack rate in the placebo arm), equivalent to an odds ratio of 0.47, power was calculated compared to the p-value of 0.05 based on 2000 simulations in 1248 subjects from 430 households (ie, assuming an average household size of 2.9 seronegative subjects). [Table 9](#) provides power calculations by varying degrees of correlation within household. In all cases, the power of the study is >90% using a generalized linear model with the generalized estimation equation (GEE) approach and assuming a compound symmetry covariance matrix.

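### Cohort A's stated power above 90% for a halved risk rests on an assumed 10% placebo symptomatic rate that is not reconciled with the trial's own 3.6%

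*Protocol*

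**What the plan says.** Protocol 11.2.1 aims for at least 90% power, two-sided, in seronegative cohort A subjects. It discounts the 100% reduction seen in the administrative assessment to a reduction of about 50% or more, because that assessment was small. It then takes a "50% reduction of the assumed 10% attack rate in the placebo arm" and simulates 1248 subjects in 430 households. Table 9 (SAP Table 1) has six rows, all 10% versus 5%, with household correlation from 0.1 to 0.6 and power from 0.914 to 0.999. The synopsis, 11.2.1 and SAP 2.2.1 all summarise this as power above 90% throughout.

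Other sections bear on the 10%:

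- Protocol 11.2: "An administrative assessment for assumption verification and sample size estimation for cohort A was conducted using unblinded descriptive analyses".
- Protocol 3.2.5 gives the assessment's result for the present primary endpoint: "8/223 (3.6%) placebo treated subjects developing symptomatic infection versus 0/186 (0%) REGN10933+REGN10987 treated subjects".
- Protocol 3.2.2 describes household contacts as at high risk, "with transmission rates ranging from approximately 10% to 15% in these settings", and says that "approximately 15% of subjects were expected to develop symptomatic disease in follow-up after a household contact transmission event". After blinded review of roughly the first quarter of subjects, it adds that "a minority of cohort A subjects who became infected during the 28 day efficacy assessment period were symptomatic".
- SAP 2.2.1 says that household correlation and serology rates will be monitored, together with the 90% cohort A share and the 70% seronegative share, so that about 1248 seronegative subjects are reached. It says this keeps power as planned. The symptomatic event rate is not on that list.

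**The concern.** Power for a binary endpoint is driven by the number of events, so the placebo rate matters at least as much as the household correlation. The plan varies the correlation and holds the rate at a single value. The sample-size text gives no source for that value, and it lies above the whole confidence interval from the trial's own data. The assessment's effect estimate was carried into the calculation, with a discount; its placebo rate for the same endpoint was not.

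What is at stake is how the result is read. If the primary comparison were non-significant or imprecise, a reader would be told that the study had more than 90% power to detect a halving of risk. The SAP adds the assurance that reaching the target number of seronegative subjects is enough to preserve that power.

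**Working it through.** **Inputs.** Two-sided alpha 0.05 and 1:1 allocation (Protocol 11.2.1, 11.4.4). N=1248, or 624 per arm (11.2.1). Observed placebo rate 8/223 = 3.59% (3.2.5). The first-step analysis has about 2459 subjects (SAP 2.1). The documents do not state its seronegative cohort A number, so two assumptions are used:
- 2459 × 0.9 × 0.7 = 1549, from the SAP's planned shares
- 2459 × 0.9 × 409/554 = 1634, from the seronegative share in the assessment

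**1. Reproduce the plan.** With n per arm and p̄ the mean of the two rates, power = Φ{[|p1 − p2|√n − 1.96√(2p̄(1 − p̄))] / √(p1(1 − p1) + p2(1 − p2))}.

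For 10% versus 5% and n=624: (1.249 − 0.730)/0.371 = 1.40, so power is 0.919. Table 9 has 0.914 at correlation 0.1. A GEE simulation gave 0.93, 0.95 and 0.99 at correlations 0.1, 0.3 and 0.6, against Table 9's 0.914, 0.956 and 0.999. The simulation used a logit link, exchangeable correlation, robust standard errors, treatment only, latent-normal correlated binary data and individual randomisation. Table 9 is sound on its own inputs.

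**2. How far 3.6% is from 10%.** The exact 95% CI for 8/223 is 1.6% to 6.9%. The probability of 8 or fewer events in 223 at a true 10% is 0.0003. Both assume independent subjects.

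**3. Same formula at 3.6% versus 1.8%.** For n=624: (0.4481 − 0.4485)/0.228 ≈ 0, so power is 0.50. Closed-form power at relative risk (RR) 0.5:

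| N | 2% | 3.6% | 5% | 7% | 10% |
|---|---|---|---|---|---|
| 1248 | 0.31 | 0.50 | 0.64 | 0.79 | 0.92 |
| 1549 | 0.37 | 0.59 | 0.74 | 0.87 | 0.96 |
| 1634 | 0.38 | 0.61 | 0.76 | 0.89 | 0.97 |

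Expected events with N=1248: 624 × (0.036 + 0.018) = 33.7, against 624 × (0.10 + 0.05) = 93.6.

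**4. GEE power at RR 0.5, by household correlation.** The plan does not give the household-size distribution. Ranges cover three assumed distributions with mean 2.9: near-equal 2/3; 1 + Poisson; 40% single-subject households. Each cell has 4000 runs, and correlation is defined between two placebo members.

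| Placebo rate | N | 0.1 | 0.3 | 0.6 |
|---|---|---|---|---|
| 3.6% | 1248 | 0.50–0.51 | 0.53–0.55 | 0.65–0.71 |
| 3.6% | 1549 | 0.58–0.60 | 0.63–0.64 | 0.78–0.81 |
| 3.6% | 1634 | 0.61–0.62 | 0.66–0.68 | 0.80–0.81 |
| 5% | 1248 | 0.64–0.65 | 0.69–0.70 | 0.82–0.86 |
| 5% | 1549 | 0.74–0.76 | 0.78–0.79 | 0.90–0.92 |
| 6.95% | 1248 | 0.80–0.81 | 0.84–0.85 | 0.94–0.95 |
| 6.95% | 1549 | 0.87–0.89 | 0.91–0.92 | 0.97–0.98 |

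**5. Definition of correlation.** SAP 6.6 indexes its power comparison on a placebo/active pair. With 0.6 defined that way and 1 + Poisson households, 10% versus 5% gives 0.999, equal to Table 9; the placebo-pair definition gives 0.993. At 3.6% this raises power at 0.6 to 0.71–0.76 (N=1248) and 0.82–0.86 (N=1549 or 1634). Every value is still below 0.90.

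**6. Effect needed for 90% at 3.6%.** Closed form: RR 0.246 (N=1248), 0.307 (N=1549), 0.322 (N=1634). GEE: RR 0.25 with N=1248 gives 0.91–0.97; RR 0.30 with N=1549 gives 0.92–0.98.

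**The case against.** The strongest reply is that the statement is already conditional. Protocol 11.2.1 calls the 10% an assumption and household symptomatic rates unknown, every row of Table 9 prints 10% and 5%, and the summary sentence follows directly on the reference to varying correlation. Read in place, it is true of the rows shown. That stands as a defence of the table. It does not cover the SAP, which says that meeting the subject count preserves power. Nor does it explain why an unknown rate was fixed while correlation was varied.

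Second, RR 0.5 is a deliberately cautious value: the assessment saw no events among 186 treated subjects. At 3.6% and RR 0.2, closed-form power is 0.94 (N=1248) or 0.97 (N=1549). This stands, and it limits the point to the stated figure. A reader might infer that the trial is underpowered; the documents do not support that, because power is adequate if the effect is much larger than a halving.

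Third, 3.6% rests on eight events in the earliest-randomised subjects and may not carry over. This also stands. A reader might infer that 10% is untenable, but Protocol 1.2 cites one US study with a 29% household attack rate, so a higher rate is possible. The plan does not make that argument.

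Fourth, a reader might divide the 8 symptomatic placebo subjects by the 21 infected placebo subjects in the viral-load statement of Protocol 3.2.6, and infer a 38% symptomatic share. No section reports that share. The same section gives 10.3% placebo positivity at day 8, and 0.103 × 223 is about 23, more than 21, so the denominator is uncertain. Nothing here relies on it.

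Finally, the first-step population is already fixed by the 28 January 2021 cutoff, so no design decision changes. That is true, and it is why the remedy is confined to the text and the table.

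**Conclusion.** Wrong as written. Table 9 and SAP Table 1 are correct for 10% versus 5%, but power above 90% for RR 0.5 holds only under a placebo rate that is neither sourced in the sample-size text nor reconciled with the trial's 3.6%. It also sits uneasily with the finding that only a minority of infected cohort A subjects had symptoms.

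At 3.6% and RR 0.5, power is about 0.50 to 0.76 with N=1248 and about 0.58 to 0.86 with N of about 1549 to 1634. The spread reflects correlation from 0.1 to 0.6, the household sizes and the definition of correlation. The larger N values and the household sizes are assumptions.

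The shortfall is clear at 3.6% but not across the whole confidence interval. Near 7%, power can pass 90% at higher correlation; at 5% it does so only with about 1549 subjects and correlation 0.6. The test, alpha, analysis set and enrolment are unaffected.

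**What to change.** - Give the source of the 10% and reconcile it with the 3.6% and with Protocol 3.2.2, or replace it.
- Add rows to Table 9 and SAP Table 1 at lower placebo rates (for example 3.6%, 5% and 7%). Use RR 0.5 and at least one smaller value (for example 0.25 to 0.3), with N=1248 and the expected seronegative N. State the household-size distribution and how correlation is defined.
- In the Protocol synopsis, Protocol 11.2.1 and SAP 2.2.1, make the power sentence conditional. For example: for RR 0.5, power exceeds 90% if the placebo symptomatic rate is 10%; at the 3.6% seen in the administrative assessment it is [range from the re-run].
- In SAP 2.2.1, replace the assurance that monitoring preserves power with a statement that power also depends on the symptomatic event rate.

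No extra enrolment is proposed. The cost is a re-run of an existing simulation with more rows. The only downside is a less favourable, conditional power statement.

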**Table 9: Simulated Power for Household Design (1248 Subjects over 430 Households)**

Placebo Attack Rate	REGN10933+REGN10987 Attack Rate	Correlation within Household	Average Odds Ratio REGN10933+REGN10987 versus Placebo	Power
10%	5%	0.1	0.485	0.914
10%	5%	0.2	0.485	0.934
10%	5%	0.3	0.480	0.956
10%	5%	0.4	0.481	0.972
10%	5%	0.5	0.476	0.983
10%	5%	0.6	0.478	0.999

At least 1980 subjects will need to be enrolled in cohort A to have a minimum of 1248 seronegative subjects, assuming that 10% of subjects drop out and 30% of subjects are seropositive at baseline.

#### **11.2.1.1. Cohort A1: Pediatric Subjects (<12 years) Who Are SARS-CoV-2 RT-qPCR Negative at Baseline**

Approximately up to a total of 250 pediatric subjects (<12 years) will be enrolled in this study. Of the 250 subjects, 90% (225/250) are expected to be enrolled in this cohort (ie, central lab RT-qPCR negative at baseline) for evaluation of the drug concentration and exposure, and safety. The actual number of subjects in this cohort will depend on the actual percentage of subjects with a baseline negative RT-qPCR enrolled. No statistical hypothesis tests will be performed.

#### **11.2.2. Cohort B: Adult and Adolescent Subjects ( $\geq 12$ years) Who Are SARS-CoV-2 RT-qPCR Positive at Baseline**

The primary endpoint in asymptomatic, seronegative subjects in cohort B is the proportion of subjects who subsequently develop signs and symptoms (broad-term) within 14 days of a positive RT-qPCR test result at baseline or during the EAP.

The sample size of cohort B is based on the frequency of finding positive subjects while enrolling cohort A and assumes that approximately 10% of subjects in a household are already positive for SARS-CoV-2 by RT-qPCR at baseline. Among approximately 3500 adult and adolescent subjects that are anticipated to be enrolled in cohort A or cohort B, the number of subjects expected in cohort B is approximately 220, including 200 seronegative subjects. Assuming that 50% of infected placebo subjects at baseline will develop symptoms, 200 seronegative subjects in cohort B will provide >90% power to detect a relative risk of 0.5 using a 2-sided Fisher's exact test at an alpha level of 0.05.

